9.3. Primary Efficacy Endpoint Analysis

9.3.1. Primary Analysis of the Primary Endpoint

The primary efficacy endpoint is the percentage of subjects with at least one CSRI, with or without an associated laboratory-confirmed pathogen, beginning at least 3 days after the start of study drug treatment through Week 16 (H₁).

The primary efficacy endpoint will be analyzed through a logistic regression model to obtain an estimate of the population odds ratio, i.e. the odds of having a CSRI in subjects treated with RTB101 compared to the odds of having a CSRI in subjects treated with placebo and its associated confidence interval. The logistic regression model will be adjusted for factors that are known to be prognostic of outcome, specifically age (continuous covariate), clinical frailty score (ordinal covariate), medical history of diabetes mellitus type 2 (T2DM, Y/N), congestive heart failure (CHF, Y/N) asthma (Y/N), and receipt of current season influenza vaccination (Y/N). Presence or absence of asthma will be obtained from medical history records and not the stratification level entered at baseline.

Analysis of the primary efficacy endpoint will be based on the estimand for the primary objective described above.

Summary statistics will be presented along with a full data listing

9.3.2. Sensitivity and Supplemental Analyses of the Primary Endpoint

The following sensitivity analyses are planned to provide evidence in support of the strength of treatment of RTB 101 10 mg as compared to placebo.

9.3.2.1. Sensitivity Analyses

For placebo subjects who discontinue study prematurely for any reason other than an RTI AE or RTI SAE and/or had ≥ 7 consecutive days of missing eDiary entries, and did not meet the definition of a CSRI, impute with CSRI odds from the placebo group, adjusted for the duration of missing eDiary entries through Week 16 in the placebo arm (as described in (1) below). For RTB101 subjects who discontinue study prematurely for any reason other than an RTI AE or RTI SAE and/or had ≥ 7 consecutive days of missing eDiary entries, and did not meet the definition of a CSRI, impute with CSRI odds that vary between that of the RTB101 odds adjusted for the duration of missing eDiary entries in the RTB101 arm, and the placebo odds. Subjects who discontinued study prematurely due to an RTI AE or RTI SAE will continue to be imputed as having a CSRI. The maximum odds that yields statistically significant results will be computed and reported as the “tipping point”.

Adjustment for the duration of missing eDiary entries in each arm will be calculated as follows:

For each arm,

- (1) Among subjects who have missing eDiary data through the Week 16 Visit, add the number of days in which subjects did not enter data in their eDiary, including only the periods that have ≥ 7

This document is confidential.

consecutive days of missing eDiary entries i.e. exclude days in which eDiary data was not entered between 1-6 days only. For subjects who discontinue study prematurely, the duration of missing eDiary entries will be calculated as the number of days from the last eDiary entry until 16 weeks after the start of study drug treatment.

- (2) Add the number of days missed in (1) for all subjects.
- (3) Calculate the total number of expected eDiary entry days for subjects with missing data, i.e. number of subjects with missing data multiplied by 111 days (16 weeks).
- (4) Divide (2) by (3).

The result obtained in (4) provides the adjustment factor used to adjust for the duration of missing eDiary entries in each arm.

1. For placebo subjects who discontinue study prematurely for any reason other than an RTI AE or RTI SAE, and did not meet the definition of a CSRI, impute with CSRI odds from the placebo group, adjusted for the duration of missing eDiary entries in the placebo arm. For RTB101 subjects who discontinue study prematurely for any reason other than an RTI AE or RTI SAE, and did not meet the definition of a CSRI, impute with CSRI odds that vary between that of the RTB101 odds, adjusted for the duration of missing eDiary entries in the RTB101 arm, and the placebo odds. Subjects who discontinued study prematurely due to an RTI AE or RTI SAE will continue to be imputed as having a CSRI. The maximum odds that yields statistically significant results will be computed and reported as the “tipping point”. Adjustment for the duration of missing eDiary entries for each arm will be calculated in the same manner as described under Sensitivity Analysis 1 above.
2. Conduct the same sensitivity analysis described in 1 above, for subjects with the following number of days with consecutive days of missing eDiary entries through the Week 16 visit:
 - a. ≥ 14 consecutive days of missing eDiary
 - b. ≥ 21 consecutive days of missing eDiary
 - c. ≥ 28 consecutive days of missing eDiary
 - d. ≥ 56 consecutive days of missing eDiary
 - e. ≥ 84 consecutive days of missing eDiary

Adjustment for the duration of missing eDiary entries for each arm will be calculated in the same manner as described under Sensitivity Analysis 1 above, with the following modifications:

- for 3a, only count subjects that have ≥ 14 consecutive days of missing eDiary entries i.e. exclude days in which eDiary data was not entered for 1-13 days when calculating the number of missed days
- for 3b, only count subjects that ≥ 21 consecutive days of missing eDiary entries i.e. exclude days in which eDiary data was not entered for 1-20 days when calculating the number of missed days.

Modify criteria for 3c-3e in a similar fashion.

9.3.2.2. *Supplemental Analyses and Summaries*

1. The primary analysis described in 9.3.1 above will be conducted in the Per Protocol (PP) population.
2. The primary analysis described in 9.3.1 above will be conducted in the subset of subjects who did not discontinue from the study prematurely and/or did not have ≥ 7 consecutive days of missing eDiary entries. (Completers Analysis 1)

This document is confidential.

3.. The primary analysis described in 9.3.1 above will be conducted in the subset of subjects who did not discontinue from the study prematurely. (Completers Analysis 2)

4.. Summary statistics (n, mean, SD, median, quartiles, minimum, maximum) and corresponding box plots by treatment group will be provided for the number of subjects with any missing data due to intermittent missed eDiary entries and premature discontinuation from the study. The number of subjects with ≥ 7 , ≥ 14 , ≥ 21 , ≥ 28 , ≥ 35 , ≥ 42 , ≥ 49 , ... ≥ 105 consecutive days of missing eDiary entries missing data will also be summarized in a similar manner.

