9.4.4. Sensitivity Analyses

9.4.4.1. Primary endpoint

To provide evidence in support of the strength of treatment effect, several sensitivity analyses will be conducted.

A tipping point analysis for the primary efficacy endpoint will be conducted to investigate the impact of the missing data assumptions on the primary endpoint results, . Missing data from the placebo arm due to early treatment discontinuation for any reason other than an RTI AE or RTI SAE and/or had ≥ 7 consecutive days of missing eDiary entries, and did not meet the definition of a CSRI, will be imputed with CSRI odds from the placebo group, adjusted for the duration of missing eDiary entries through Week 16 in the placebo arm. For RTB101 subjects who discontinue study prematurely for any reason other than an RTI AE or RTI SAE and/or had ≥ 7 consecutive days of missing eDiary entries, and did not meet the definition of a CSRI, will be

imputed with CSRI odds that vary between that of the RTB101 odds adjusted for the duration of missing eDiary entries in the RTB101 arm, and the placebo odds. Subjects who discontinued study prematurely due to an RTI AE or RTI SAE will continue to be imputed as having a CSRI.. The objective is to determine the maximum odds in the RTB101 arm that continue to yield statistically significant results compared to placebo. Further details on the above tipping point analysis and other sensitivity analyses are included in the SAP.

Supplemental analyses will also be conducted to further understand the impact of missing data on the primary efficacy endpoint results, specifically, the primary efficacy analysis will be conducted in 1) the Per Protocol analysis set, 2) the subset of subjects who did not discontinue from the study prematurely and/or did not have ≥ 7 consecutive days of missing eDiary entries (Completers Analysis 1) and 3) the subset of subjects who did not discontinue from the study prematurely (Completers Analysis 2).

Summary statistics by treatment group will be provided for the number of subjects with any missing data due to intermittent missed eDiary entries and premature discontinuation from the study. The number of subjects with ≥ 7 , ≥ 14 , ≥ 21 , ≥ 28 , ≥ 35 , ≥ 42 , ≥ 49 , ... ≥ 105 consecutive days of missing eDiary entries missing data will also be summarized in a similar manner.

Further details on handling missing data will be provided in the SAP.

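### The tipping-point sweep for the primary endpoint stops at the placebo odds, so a result still significant there is reported as a tipping point when it is only the end of the range

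*SAP*

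**What the plan says.** The primary analysis counts two groups without an observed CSRI as having none: subjects who leave the study for reasons other than an RTI adverse event, and completers with intermittent diary gaps (SAP 7.3 and 9.2.1; Protocol 9.4). The tipping-point analysis is the planned test of that assumption.

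In the main version in SAP 9.3.2.1, the subjects imputed are those who left the study for non-RTI reasons and/or had at least 7 "consecutive days of missing eDiary entries, and did not meet the definition of a CSRI". Placebo subjects get the placebo odds scaled by a duration factor: days missed divided by expected days, at 111 days per subject. RTB101 subjects get odds that run from the RTB101 odds "adjusted for the duration of missing eDiary entries in the RTB101 arm, and the placebo odds". The reporting rule is: "The maximum odds that yields statistically significant results will be computed and reported as the" tipping point.

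Item 1 repeats this for study discontinuations alone: "impute with CSRI odds that vary between that of the RTB101 odds, adjusted for the duration of missing eDiary entries", again up to the placebo odds. Item 2 carries it to gaps of at least 14 to at least 84 days: "Conduct the same sensitivity analysis described in 1 above, for subjects with the following number of days".

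Protocol 9.4.4.1 has the same range ("imputed with CSRI odds that vary between that of the RTB101 odds", up to the placebo odds) and states the purpose: "The objective is to determine the maximum odds in the RTB101 arm that continue to yield statistically significant results compared to placebo". It leaves further details to the SAP.

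Neither document says what to report if significance is never lost within the range. The SAP does not say whether the upper limit is itself duration-adjusted.

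**The concern.** A tipping point is useful because it tells the reader how bad the unseen outcomes must be before the conclusion fails. A sweep with a fixed top can supply that only if the crossing lies below the top. If the result is still significant there, the rule returns the top of the range and calls it the tipping point.

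The reader would then know that the result survives placebo-level risk in the missing RTB101 subjects. The reader would not know whether it fails at 35%, fails at 80% or never fails. The per-protocol and completers analyses in SAP 9.3.2.2 do not fill the gap: they restrict the analysis set and do not raise the imputed risk.

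**Working it through.** **Plan's own figure.** SAP 3.6 gives 1066 subjects for 90% power at 28.2% vs 19.7%, two-sided 0.05, likelihood ratio chi-square. With the unrounded 30% reduction (0.7 × 28.2% = 19.74%), a noncentral chi-square calculation gives N=1066 and power 0.900. With 19.7% the power is 0.903. The figure reproduces.

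**Inputs.**
- Planned result at 533 per arm: 105 CSRI subjects on RTB101 (19.7%) and 150 on placebo (28.1%).
- Imputed subjects per arm, m (assumed): 27 (5.1% × 533) and 36 (6.8% × 533), from the combined and Northern Hemisphere Phase 2b missing rates in Protocol 9.4.2. The Southern Hemisphere rate of 0.56% gives about 3. The documents give no rate for the group actually imputed (study discontinuation and/or gaps of at least 7 days).
- Duration factor f (assumed): 0.06 to 1, applied as a multiplier on the odds. A subject with the shortest qualifying gap contributes 7/111 = 0.06. The value 0.36 is an illustrative midpoint.
- Upper limit (assumed): the unadjusted placebo odds, 150/383 = 0.392, a risk of 0.281.

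**Method.** Unadjusted two-proportion z test on expected counts. Placebo imputed risk q = 0.392f/(1 + 0.392f). Placebo events = 150 + mq. RTB101 events = 105 + mr, where r is the swept risk. z = (difference in proportions)/√(2p̄(1−p̄)/533).

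**Before imputation.** Difference 45/533 = 0.0844; p̄ = 255/1066 = 0.239; SE = 0.0261; z = 3.23; p = 0.0012.

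**One case in full (m=36, f=0.06).** q = 0.0235/1.0235 = 0.0230. Placebo events 150 + 0.83 = 150.83. At the limit, RTB101 events 105 + 36 × 0.2814 = 115.13. p̄ = 265.96/1066 = 0.2495; SE = 0.0265; difference 35.70/533 = 0.0670; z = 2.53; p = 0.0115. Raising r until z = 1.96 gives r = 0.496 (122.87 events, difference 0.0525, SE 0.0268).

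| m | f | q | Placebo events | RTB101 events at limit | p at limit | r at crossing |
|---|---|---|---|---|---|---|
| 27 | 0.06 | 0.023 | 150.62 | 112.60 | 0.0069 | 0.65 |
| 27 | 0.36 | 0.124 | 153.34 | 112.60 | 0.0039 | 0.75 |
| 27 | 1 | 0.281 | 157.60 | 112.60 | 0.0015 | 0.90 |
| 36 | 0.06 | 0.023 | 150.83 | 115.13 | 0.0115 | 0.50 |
| 36 | 0.36 | 0.124 | 154.45 | 115.13 | 0.0056 | 0.59 |
| 36 | 1 | 0.281 | 160.13 | 115.13 | 0.0016 | 0.74 |

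**Few imputed (m=3, f=0.06).** Setting all three RTB101 subjects to CSRI gives 108 vs 150.07, p = 0.0026. No crossing exists.

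**If the limit is duration-adjusted.** At m=36, f=0.06, RTB101 events at the limit are 105.83 against 150.83, p = 0.0013. The crossing is unchanged, so it lies further outside the range.

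**Where the present range does find the crossing (unadjusted limit).**
- Heavy missingness with a low duration factor: from 66 per arm (12%) at f=0.06 and from 104 (20%) at f=0.36. With 80 per arm and f=0.06 the limit p is 0.09. At f=1 the planned effect never crosses inside the range.
- A marginal primary result: with 27 to 36 imputed per arm, an observed relative reduction of about 19% to 25%. For example, 113 vs 150 has primary p = 0.009 and, at m=36 and f=0.06, limit p = 0.052.

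**Robustness.** Adding between-imputation variance moves the limit p to 0.0020–0.0078 (m=27) and 0.0023–0.0133 (m=36), and the crossing to 0.64–0.88 and 0.48–0.71. In simulated trials at the planned effect, over f = 0.06 to 1, significant trials divide as follows:

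| m | Crossing beyond limit | Inside range | None exists |
|---|---|---|---|
| 3 | 3.5–3.7% | 0.1–1.1% | 95–96% |
| 27 | 51–59% | 0.7–13% | 28–48% |
| 36 | 71–73% | 1–19% | 10–28% |

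**The case against.** **Stopping at the placebo odds is a recognisable choice.** It asks whether the result survives if missing subjects got no benefit from the drug. In Protocol 9.4.4.1 the objective closes the same paragraph that sets the range, so it can be read as the maximum within that range. This stands in part. A reader might infer that the SAP contradicts the protocol, but the two agree on range and rule. What remains is that neither covers a sweep that never tips.

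**The limit can already be severe.** On the unadjusted reading with f=0.06, missing RTB101 subjects get about 12 times the imputed placebo risk (0.281/0.023). At f=0.36 the ratio is 2.3, and at f=1 it is 1. This stands for that reading only.

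**The sweep works where the result is fragile.** This also stands. A reader might infer that the analysis can never find a crossing, and the figures above show otherwise.

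**The missing rate may be too high.** SAP 2.2 places the Week 16 analysis before a second trial enrols in the northern winter. That hints, without stating it, that this trial runs in a southern winter. At the 0.56% Southern Hemisphere rate there is nothing to find. Gaps of at least 7 days could be commoner than that, and the documents do not settle it.

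**A careful reader would recognise the placebo odds as the limit.** True, but that does not reveal where the conclusion fails.

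**Conclusion.** The point holds as a low-cost improvement to a sensitivity analysis. When the result is still significant at the placebo odds, the planned rule labels the end of the range a tipping point. At the planned effect with 27 to 36 imputed per arm, that is the usual outcome of a significant trial: p at the limit is 0.0015 to 0.0115, and the crossing is at an imputed risk of about 0.50 to 0.90.

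Those limit p-values rest on three assumptions: the number imputed, the duration factor and an unadjusted upper limit. The crossing values rest on the first two. All come from unadjusted tests, not the covariate-adjusted logistic model.

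A reader might infer that the primary result is in doubt. The documents do not support that: the primary analysis and its p-value are untouched, and in these scenarios the longer sweep would show a more robust result than the plan can report.

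**What to change.** In SAP 9.3.2.1, for the main analysis and items 1 and 2:
- Sweep the imputed CSRI probability for eligible RTB101 subjects up to 100%.
- Report the value at which two-sided p crosses 0.05, or state that none exists.
- Show the result at the placebo odds as a labelled reference point, and say whether those odds are duration-adjusted.

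No protocol amendment is needed, since Protocol 9.4.4.1 leaves the details to the SAP. The extension can be listed in SAP Section 12.

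The cost is a longer loop in the same program and one more table or curve. Some swept values will be clinically implausible, which is why the placebo-odds result should sit beside the crossing. With very few imputed subjects, the change only replaces a range-end value with a statement that no tipping point exists.

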9.4. Analyses of Secondary Efficacy Endpoints

9.4.1. Percentage of Subjects with One or More Clinically Symptomatic Respiratory Illnesses Associated with ≥ 1 Laboratory-confirmed Pathogen(s)

The percentage of subjects with CSRI associated with ≥ 1 laboratory-confirmed pathogen(s) beginning at least 3 days after the start of study drug treatment through Week 16 (H_2) as assessed by pre-specified clinical diagnostic criteria and respiratory pathogen PCR of nasopharyngeal swabs, sputum gram stain and culture, and/or RIDTs will be analyzed in the same manner as the primary efficacy analysis as described in 9.3.1 based on the estimand for the secondary objective corresponding to this endpoint described in 9.2.2 above.

Laboratory results from a specimen obtained within 3 days before the CSRI start date through the CSRI end date will be used to determine if the CSRI is associated with ≥ 1 laboratory-confirmed pathogen. Laboratory confirmation includes a positive respiratory pathogen PCR of nasopharyngeal swabs, sputum gram stain and culture, and/or RIDT. If multiple specimens are obtained for a particular CSRI, then any positive result will be counted as laboratory confirmation if it occurs within 3 days before the CSRI start date through the CSRI end date. A laboratory-confirmed CSRI may be associated with multiple pathogens. Note that organisms considered to identify a positive sputum specimen should meet standard microbiological laboratory criteria of growing from a sputum specimen with > 25 WBC/hpf and < 10 Squamous cells/ hpf, and they have matching morphology on gram stain and culture.

Summary statistics will be presented along with a full data listing by treatment group.

9.4.2. Rate of Clinically Symptomatic Respiratory Illnesses (with or without an Associated Laboratory-confirmed Pathogen)

The rate of CSRI (with or without an associated laboratory-confirmed pathogen) beginning at least 3 days after the start of study drug treatment through Week 16 (H_3) will be analyzed based on the negative binomial distribution. The first 3 days of study drug treatment will not be included in determining the denominator of rate.

A generalized linear model analysis will be conducted using the number of CSRI per 16-week period (illnesses/16 weeks) as the dependent variable and will include treatment group, age (continuous covariate), Clinical Frailty Scale score (ordinal covariate), medical history of diabetes mellitus type 2 (Y/N), medical history of asthma (Y/N) medical history of CHF (Y/N), and receipt of current season influenza vaccination (Y/N) as fixed effects.

This document is confidential.

The rate ratio (RR) (RTB101 dose group to placebo) of the treatment effect will be derived from the model along with the 95% 2-sided confidence interval (CI). Model-adjusted mean rates for each treatment group and their corresponding 95% 2-sided CI will also be calculated.

The “log” link function will be used in the model and an offset term will be included to account for variable lengths of treatment exposure across the subjects. The unadjusted rate of CSRI per subject through Week 16 will be calculated by summing the number of total CSRIs per subject through Week 16 within each treatment group.

Analysis of this endpoint will be based on the estimand for the secondary objective corresponding to this endpoint described in 9.2.2 above.

Summary statistics will be presented along with a full data listing by treatment group.

9.4.3. Rate of Clinically Symptomatic Respiratory Illness Associated with ≥ 1 Laboratory-confirmed Pathogen(s)

The rate of CSRIs associated with ≥ 1 laboratory-confirmed pathogen(s) beginning at least 3 days after the start of study drug treatment through Week 16 (**H₄**) as assessed by pre-specified clinical diagnostic criteria and respiratory pathogen PCR of nasopharyngeal swabs, sputum gram stain and culture, and/or RIDTs will be analyzed in the same manner as described in 9.4.2 above, based on the estimand for the secondary objective corresponding to this endpoint described in 9.2.2 above. Section 9.4.1 describes which laboratory result will be used to determine if the CSRI is associated with ≥ 1 laboratory-confirmed pathogen.

Summary statistics will be presented along with a full data listing by treatment group.

